During the iv PK Period, iv BRV will be administered every 12 hours ± 2 hours (q12h ± 2 h). All subjects will receive 1 to 2 consecutive doses of BRV; however, based on medical need, subjects may receive up to 10 consecutive doses of iv BRV. Blood sampling for PK analyses (herein referred to as "PK sampling") will occur with the first iv BRV administration and with 1 other iv BRV administration. For OLB, RxB, and IOB subjects, the first iv BRV dose will be equivalent

(mg-to-mg) to the final dose of oral BRV prior to the first iv dose. For IIB subjects, the first iv BRV dose will be 1mg/kg, not to exceed 50mg for subjects with body weights ≥ 50 kg. For all subjects, iv BRV doses may be adjusted at the Investigator's discretion after PK sampling for 2 iv doses; however, no doses may exceed the maximum doses indicated below. During the iv PK Period, BRV may only be administered by iv infusion.

At the completion of the iv PK Period, subjects who will continue oral BRV treatment should enroll in a long-term, open-label BRV study. Subjects who have received ≥ 4 doses of BRV and do not plan to continue treatment with BRV after completion of the iv PK Period or who discontinue BRV treatment during the study will have a Down-Titration Period of up to 4 weeks (28 days) for gradual discontinuation of BRV and a Safety (BRV-free) Period of 2 weeks (14 days) after the final dose of BRV. Subjects who have received < 4 doses of BRV may have BRV down titrated at the discretion of the Investigator.

For IOB and IIB subjects, the maximum BRV dose is 4mg/kg/day (2mg/kg twice daily [bid]). For OLB and RxB subjects, the maximum BRV dose is 5mg/kg/day (rounded) in recognition of the possibility that some of these subjects may be using this dose when they enter EP0065.

Throughout the study, no subjects may receive a dose greater than BRV 200mg/day. Oral BRV will be administered in equally divided doses bid.

It is planned for approximately 50 enrolled subjects to receive iv BRV in the following age-based cohorts (approximately 12 subjects/cohort), with approximately half of the subjects in each cohort receiving iv BRV as a 15-minute (± 3 minutes) infusion and half receiving iv BRV as a bolus (up to 2-minute infusion).

- Cohort 1: ≥ 12 to < 16 years
- Cohort 2: ≥ 6 years to < 12 years
- Cohort 3: ≥ 2 to < 6 years
- Cohort 4: 1 month to < 2 years

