 - Investigators should attempt to obtain information on subjects in the case of withdrawal; subjects who withdraw from the study without down titration of BRV should complete the Visit 13 (Table 5–4).

For subjects considered lost to follow up, the Investigator should make an effort (at least 1 phone call and 1 written message to the subject), and document his/her effort (date and summary of the phone call and copy of the written message in the source documents), to complete the final evaluation. All results of these evaluations and observations, together with a narrative description of the reason(s) for removing the subject, must be recorded in the source documents. The CRF must document the primary reason for withdrawal.

Investigators should contact the Medical Monitor, whenever possible, to discuss the withdrawal of a subject in advance.

6.3.1 Potential drug-induced liver injury investigational medicinal product discontinuation criteria

Subjects with potential drug-induced liver injury (PDILI) must be assessed to determine if the investigational medicinal product (IMP) must be discontinued. In addition, all concomitant medications and herbal supplements that are not medically necessary should also be discontinued.

The PDILI criteria below require immediate and permanent discontinuation of IMP:

- Subjects with either of the following:
 - ALT or AST $\geq 5 \times \text{ULN}$
 - ALT or AST $\geq 3 \times \text{ULN}$ and coexisting total bilirubin $\geq 2 \times \text{ULN}$

The PDILI criterion below requires immediate discontinuation of IMP:

- Subjects with ALT or AST $\geq 3 \times \text{ULN}$ who exhibit temporally associated symptoms of hepatitis or hypersensitivity. Hepatitis symptoms include fatigue, nausea, vomiting, right upper quadrant pain or tenderness. Hypersensitivity symptoms include fever (without clear alternative cause), rash, or eosinophilia (ie, $>5\%$).

The PDILI criterion below allows for subjects to continue on IMP at the discretion of the Investigator.

- Subjects with ALT or AST $\geq 3 \times \text{ULN}$ (and $\geq 2 \times$ baseline) and $< 5 \times \text{ULN}$, total bilirubin $< 2 \times \text{ULN}$, and no eosinophilia (ie, $\leq 5\%$), with no fever, rash, or symptoms of hepatitis (eg, fatigue, nausea, vomiting, right upper quadrant pain or tenderness).

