7.2.2 Down-Titration Period

All subjects who have received ≥ 4 doses of BRV during either the IOB Treatment Period or the iv PK Period and who will not continue BRV will have their BRV dose reduced by a maximum of half the dose every week for a maximum of 4 weeks until a dose of 1mg/kg/day (50mg for subjects with body weights ≥ 50 kg) is reached. Subjects who have received < 4 doses of BRV may have BRV down titrated at the discretion of the Investigator. Subjects not able to receive oral BRV for down titration, may receive iv BRV for down titration. In the later circumstance, the subjects may receive more than 10 consecutive doses of iv BRV in accordance with the Investigator's discretion.

The OLB subjects who discontinue BRV during the Screening Period will return to the long-term, open-label study for down titration of BRV.

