10.1.4 Pregnancy

If an Investigator is notified that a subject has become pregnant after the first intake of any IMP, the Investigator must immediately notify UCB's PS department by providing the completed Pregnancy Report and Outcome form (for contact details see SAE reporting information at the beginning of this protocol). The subject should be withdrawn from the study as soon as pregnancy is known (by positive pregnancy test), and the following should be completed:

- The subject should immediately stop the intake of BRV or be down-titrated as instructed by the Investigator.
- For subjects who have BRV down-titrated:
 - Return for Visit 13.
 - TC-3 should be scheduled 2 weeks after the subject has discontinued BRV.

The Investigator must inform the subject of information currently known about potential risks and about available treatment alternatives.

The pregnancy will be documented on the Pregnancy Report and Outcome form provided to the Investigator. The progression of the pregnancy and the eventual birth (if applicable) must be followed up using the Pregnancy Report and Outcome form in which the Investigator has to report on the health of the mother and of the child. Every reasonable attempt should be made to follow the health of the child for 30 days after birth for any significant medical issues. In certain circumstances, UCB may request that follow up is continued for a period longer than 30 days. If the subject is lost to follow up and/or refuses to give information, written documentation of attempts to contact the subject needs to be provided by the Investigator and filed at the site. UCB's PS department is the primary contact for any questions related to the data collection for the pregnancy, eventual birth, and follow up.

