10.2.1 Evaluation of PDILI

The PDILI IMP discontinuation criteria for this study are provided in Section 6.3.1, with the accompanying required follow-up investigation and monitoring detailed below. All PDILI events must be reported as an AE and reported to the study site and Sponsor within 24 hours of learning

of their occurrence. Any PDILI event that meets the criterion for potential Hy's Law must be reported as an AE of special interest (see Section 10.1.1.3), and, if applicable, also reported as an SAE (see Section 10.1.2.3).

Evaluation of PDILI consists of the diagnostic testing and continued monitoring included in Table 10-3 (specific tests dependent on laboratory results and corresponding symptoms) and consultation with a local hepatologist (if applicable; discussed in Section 10.2.1.1). The local hepatologist is the expert usually consulted by the treating physician for assessment and management of potential hepatic disease. This would usually be a hepatologist, but may be a gastroenterologist. Additional investigation and monitoring may be required and adapted based on the diagnosis after the cause of the liver injury/abnormality is confirmed (details in Section 10.2.1.4).

The results of all monitoring, including laboratory testing and other testing, should be made available to the study site and Sponsor.

All initial tests resulting in abnormal hepatic laboratory values need to be repeated, but appropriate medical action must not be delayed waiting for the repeat result.

If tests are done locally for more rapid results, a concurrent sample should also be sent to the central laboratory whenever possible. Medical care decisions are to be made initially using the most rapidly available results and a conservative approach must be taken if the results from the 2 laboratory tests are significantly different. Data from the local and central laboratory are to be recorded on the applicable CRF pages.

When IMP is discontinued, all concomitant medications and herbal supplements that are not medically necessary should also be discontinued. In these cases, the Investigator should also consider dose reduction for medically necessary concomitant medication and consider changing any medically required concomitant medication known to be hepatotoxic to a suitable alternative.

Rechallenge with a substance potentially causing drug-induced liver injury is dangerous, may be fatal, and must not occur.

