The table below summarizes the approach to investigate PDILI.

Table 10–3: Required investigations and follow up for PDILI

Laboratory value			Immediate		Follow up	
ALT or AST	Total bilirubin	Symptoms ^a of hepatitis or hypersensitivity	Consultation requirements	Actions	Testing	Evaluation
≥3xULN	≥2xULN ^b	NA	Hepatology consult. ^c Medical Monitor must be notified within 24 hours (eg, by laboratory alert) and subject discussed with Medical Monitor ASAP.	Immediate, permanent IMP discontinuation.	Essential: Must have repeat liver chemistry values and additional testing completed ASAP (see Section 10.2.1.3); recommended to occur at the site with HCP.	Monitoring of liver chemistry values at least twice per week until values normalize, stabilize, or return to within baseline values. ^d
≥3xULN	NA	Yes		Immediate, temporary or permanent, IMP discontinuation.		
≥5xULN (and ≥2x baseline)	<2xULN	No	Discussion with Medical Monitor required. Hepatology consult required if ALT/AST ≥8x ULN.	Immediate, permanent IMP discontinuation.	Essential: Every attempt must be made to have repeat liver chemistry values and additional testing completed within 48 hours at the site with HCP (see Section 10.2.1.3).	

Table 10–3: Required investigations and follow up for PDILI

Laboratory value			Immediate		Follow up	
ALT or AST	Total bilirubin	Symptoms ^a of hepatitis or hypersensitivity	Consultation requirements	Actions	Testing	Evaluation

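### For children with at least 4 BRV doses who meet a liver-injury stop criterion, the protocol does not reconcile the immediate stop with the unqualified taper rule, or a temporary stop with the rechallenge ban

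*Protocol*

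**What the plan says.** **Stop rules.** Protocol 6.3.1 sets three tiers.

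- ALT or AST of at least 5xULN, or at least 3xULN with total bilirubin of at least 2xULN: "The PDILI criteria below require immediate and permanent discontinuation of IMP".
- ALT or AST of at least 3xULN with symptoms of hepatitis or hypersensitivity: "The PDILI criterion below requires immediate discontinuation of IMP". Permanence is not mentioned.
- Asymptomatic elevation from 3x to below 5xULN, with the other listed conditions: "The PDILI criterion below allows for subjects to continue on IMP at the discretion of the Investigator".

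Table 10-3 restates these tiers. For the symptomatic row its action is "Immediate, temporary or permanent, IMP discontinuation".

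**Taper rule.** Section 7.2.2 covers all subjects with at least 4 doses in the IOB Treatment or iv PK Period "who will not continue BRV will have their BRV dose reduced by a maximum of half the dose every week". The Summary extends the rule to those "or who discontinue BRV treatment during the study will have a Down-Titration Period of up to 4 weeks (28 days". Section 5.1 also sends subjects with at least 4 doses into the Down-Titration Period if they do not plan to continue BRV or if they leave the study. Below 4 doses the taper is left to the Investigator. SAP 2.3 repeats the Section 5.1 text and adds no PDILI exception.

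**Rechallenge.** Section 10.2.1 states: "Rechallenge with a substance potentially causing drug-induced liver injury is dangerous, may be fatal, and must not occur".

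**Pregnancy.** Section 10.1.4 does settle stopping against tapering for that event: "The subject should immediately stop the intake of BRV or be down-titrated as instructed by the Investigator".

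**The concern.** The taper passages are written as requirements, and the stop passages are written as requirements. A site with a child who has had at least 4 doses and meets a stop criterion finds both in the same protocol, with no sentence saying which gives way. Under one, no further BRV is given. Under the other, a drug suspected of injuring the liver continues at falling doses. Whichever the site follows, the other passage makes it a deviation, and sites may differ.

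The handling of the data would differ too. Under SAP 3.2.5, only subjects who down-titrate have a Safety (BRV-free) Period, and the end of the Follow-up Period depends on whether a taper was given. The same clinical event could therefore be filed under different analysis periods according to how the site resolved the conflict.

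The symptomatic row raises a second question. A temporary stop leaves room for a restart, and the rechallenge statement carries no exception.

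**Working it through.** No sample size, power or alpha enters this point. The check is a comparison of passages plus a count of doses.

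**Step 1. Is the taper further investigational product?** Protocol 7.1 lists the tablets, the oral solution and the iv solution as investigational medicinal products. The SAP (2.3) reserves the term study medication for iv BRV, but that is an analysis convention and does not change what 6.3.1 tells a site to stop. A taper, oral or iv, is therefore further dosing with the product that 6.3.1 says to discontinue.

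**Step 2. Which PDILI cases meet both rules?**

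| Case | Stop text | Taper text | Both apply? |
|---|---|---|---|
| At least 5xULN, or at least 3xULN with bilirubin at least 2xULN; at least 4 doses | Immediate and permanent | Will be tapered | Yes |
| Symptomatic, at least 3xULN; at least 4 doses | Immediate | Will be tapered, if BRV is not to continue | Yes |
| Any stop criterion; fewer than 4 doses | Immediate | Discretionary | No binding conflict |
| Asymptomatic, 3x to below 5xULN, allowed to continue | None at once | Not triggered | No |

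**Step 3. Who reaches 4 doses?**

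- IOB subjects: at least 2 days of oral BRV x 2 doses per day = 4 doses. A subject who completes the minimum meets the threshold.
- OLB, RxB and IIB subjects: Sections 5.1 and 7.2.2 count doses in the IOB Treatment or iv PK Period. The usual 1 to 2 iv doses fall short; these subjects need at least 4 of the up to 10 iv doses allowed on medical need.
- The Summary names no period for its count, so OLB and RxB subjects already on oral BRV could meet it there.

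**Step 4. Size of the difference in exposure.**

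- Under the stop text: 0 further days.
- Under the taper text: at most 28 days x 2 doses per day = 56 doses.
- The taper ends at 1 mg/kg/day for subjects below 50 kg. With the largest permitted step, the IOB starting dose gets there in one reduction (2 x 1/2 = 1 mg/kg/day), and 4 mg/kg/day in two (4 x 1/2 x 1/2 = 1). A full 28 days is therefore not the expected length. The documents fix only the maximum.

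**Step 5. Do other passages resolve it?**

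- Section 10.2.1.2 refers sites to 6.3.1 and Table 10-3 for the immediate action. It does not say that these override the taper.
- Sections 6.3 and 8.6 foresee withdrawal without down-titration. Section 8.6 does not define who does not need a taper. Both concern leaving the study, while 6.3.1 says PDILI subjects should stay in until investigation and monitoring are finished.
- The pregnancy sentence in 10.1.4 has no PDILI counterpart.

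**Step 6. Temporary stop against the rechallenge ban.** The permanent-stop rows agree with the ban. Only the symptomatic row is open: Table 10-3 allows a temporary stop, 6.3.1 is silent on permanence, and 10.2.1 bans rechallenge with a substance potentially causing liver injury. No passage gives the condition under which a temporary stop fits the ban.

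**Step 7. How would a case be found?** Clinical chemistry is scheduled at Visit 1 (Table 5-1), where exclusion criterion 14 applies, and at Visit 13 (Table 5-4), where oral BRV is collected. A stop during dosing would mostly arise from an unscheduled test.

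**The case against.** The best reply is that the protocol is built as a general taper rule plus event-specific sections. Section 10.2.1.2 names 6.3.1 and Table 10-3 as the place to look, and the pregnancy section works in the same way without any carve-out in 7.2.2. A sensible site would treat the specific text as governing, and the references to withdrawal without down-titration show that the taper is not universal.

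Part of this stands. The absence of an exception inside 7.2.2 is not by itself a contradiction, and many sites might reach the same answer. But the pregnancy section mentions the taper and says how it relates to the stop; the PDILI sections never mention it. The withdrawal route is also held back for PDILI subjects until their work-up ends.

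On rechallenge, the reply is that a temporary stop is a permission. It could mean a restart only after another cause has been found, since 10.2.1.3 is about identifying or excluding one. That reading is plausible, but the text does not state it.

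Four stronger readings are tempting and are not supported:

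- **That every PDILI case meets opposite binding instructions.** The taper is discretionary below 4 doses, and some cases may continue.
- **That the protocol orders a re-exposure.** Nothing instructs a restart.
- **That 6.3.1 and Table 10-3 disagree on permanence in the symptomatic row.** Silence on permanence is compatible with temporary or permanent.
- **That affected children would typically receive 28 more days of BRV.** That figure is the maximum.

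**Conclusion.** The point holds in a narrow form. For subjects with at least 4 doses who meet a PDILI stop criterion, the stop text and the taper text cannot both be followed as written, and no passage ranks them. For symptomatic ALT or AST of at least 3xULN, the permission for a temporary stop is not reconciled with an unconditional ban on rechallenge.

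The difference in further exposure is 0 days against at most 28 days (56 doses). It rests on twice-daily dosing and on the maximum taper length. The documents give no expected number of PDILI cases. With about 50 children and no chemistry scheduled between Visits 1 and 13, few are likely to surface during dosing. That limits how often the conflict would arise, but does not remove it. No effect on the PK or adverse event estimates has been shown. The reason to act is that the setting is suspected liver injury in a child and the correction is simple. No view is taken here on which clinical rule is right.

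**What to change.** In one amendment, reconcile the Summary, Section 5.1, Section 7.2.2, Section 6.3.1, Table 10-3 and Section 10.2.1:

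- State in each relevant place the same relation between PDILI discontinuation and down-titration, including for subjects who remain in the study during work-up.
- Make the action for the symptomatic row (ALT or AST of at least 3xULN) consistent with the rechallenge statement.
- Carry the result into SAP 2.3, which repeats the taper text.

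The sponsor's medical team decides which rule holds.

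As an editorial item, correct the pointer in 10.2.1.4. It sends sites to Table 10-4 for follow-up monitoring, but that table lists diagnostic tests; the monitoring schedule is in Table 10-3, to which 10.2.1 already refers.

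The cost is wording only: no added visits, tests or subjects.

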7 STUDY TREATMENT(S)

7.1 Description of investigational medicinal products

Information pertaining to excipients and tablet coatings for the IMP used in this study is provided in the Investigator's Brochure.

7.1.1 Film-coated tablets for oral administration

Tablet strengths: BRV 10mg, 25mg, 50mg, 75mg, and 100mg

7.1.2 Oral solution

Concentration: BRV 10mg/mL

7.1.3 Solution for iv injection

Concentration: BRV 10mg/mL

7.2 Treatments to be administered

For BRV tablets, the mg dosage for the oral tablet treatment should be calculated to match as closely as possible the mg/kg based dosage. Tablets of BRV 10mg, 25mg, 50mg, 75mg, and 100mg are supplied and may be combined, as needed, to achieve the calculated mg/kg dose. Tablets and solution must not be used together to comprise an individual dose.

The dose of oral solution will be measured using the appropriate syringes (1mL, 3mL, and/or 10mL) with an adaptor able to fit the bottle sizes. Oral solution should not be mixed with other liquids prior to administration.

For 15-min iv infusions, a calibrated infusion pump should be used for delivering the iv BRV dose at a constant rate over the target duration assigned. A previously unused vial must be administered for each dose. Dilution is not required prior to administration of iv BRV. The BRV solution for iv injection can be diluted as needed in any of the following diluents:

- 0.9% sodium chloride injection
- Lactated Ringer's injection
- 5% dextrose injection

The total volume of diluent should be calculated not to exceed a total volume of fluid intake/day based on the Holliday-Segar equation as follows:

- For children weighing ≤ 10 kg: 100mL/kg body weight
- For children weighing > 10 to ≤ 20 kg: 1000mL + 50mL/kg for each kg body weight ≥ 10 kg

- For children weighing $\geq 20\text{kg}$: $1500\text{mL} + 20\text{mL/kg}$ for each kg body weight $\geq 20\text{kg}$
Brivaracetam will be dispensed using interactive response technology (IRT).

7.2.1 Screening, IOB Treatment, and iv PK Periods

Dosing information for BRV during the Screening, IOB Treatment, and iv PK Periods is provided in [Table 7-1](#).

Table 7-1: BRV dosing during the Screening, IOB Treatment, and iv PK Periods

	Study Period				
	Screening (1-10 days)	IOB Treatment (2-10 days) ^a	iv PK (1-6 days) ^b		
Subjects	Dose (oral)	Dose (oral)	First dose (iv)	Subsequent dose(s) (iv)	Maximum BRV Dose
OLB	Per Long-Term, Open-Label study	N/A	mg-to-mg equivalent to last oral dose	Equivalent to first iv dose until PK sampling is completed.	5mg/kg/day (rounded) nte. 200mg/day for body weight $\geq 40\text{kg}$
RxB	As prescribed	N/A	mg-to-mg equivalent to last oral dose	Equivalent to first iv dose until PK sampling is completed.	5mg/kg/day (rounded) nte. 200mg/day for body weight $\geq 40\text{kg}$
IOB	Not receiving BRV	Subjects $< 50\text{kg}$: 2mg/kg/day Subjects $\geq 50\text{kg}$: nte. 100mg/day	mg-to-mg equivalent to last oral dose	Equivalent to first iv dose until PK sampling is completed.	4mg/kg/day nte. 200mg/day for body weight $\geq 50\text{kg}$
IIB	Not receiving BRV	N/A	Subjects $< 50\text{kg}$: 1mg/kg Subjects $\geq 50\text{kg}$: 50mg	Equivalent to first iv dose until PK sampling is completed.	4mg/kg/day nte. 200mg/day for body weight $\geq 50\text{kg}$

	Study Period				
	Screening (1-10 days)	IOB Treatment (2-10 days) ^a	iv PK (1-6 days) ^b		
Subjects	Dose (oral)	Dose (oral)	First dose (iv)	Subsequent dose(s) (iv)	Maximum BRV Dose

bid=twice daily; BRV=brivaracetam; IIB=Initiating iv BRV; IOB=Initiating Oral BRV; iv=intravenous;

LT=Long-term; N/A=not applicable; nte.=not to exceed; OL=Open-label; OLB=Open-label BRV;

PK=pharmacokinetic; q12h=every 12 hours; RxB=Prescribed BRV

Note: Oral BRV will be administered in equally divided doses bid as either tablets or oral solution. Tablets will be administered orally and oral solution will be administered either orally or by enteric administration (eg, feeding tube) based on subject need.

Note: Intravenous BRV will be administered as a 15-minute (± 3 minutes) infusion or bolus (up to 2-minute infusion), as assigned and will be administered q12hours ± 2 hours.

^a Dose adjustment is allowed at the Investigator's discretion provided the adjusted dose does not exceed the maximum dose indicated in the rightmost column of this table and does not occur within 2 days of entry into the iv PK Period.

^b Dose adjustment is allowed at the Investigator's discretion provided that PK sampling has been completed for 2 doses and the adjusted dose does not exceed the maximum dose indicated in the rightmost column of this table and does not occur within 2 days of entry into the iv PK Period.

